## **2. Study Purpose**

Comparing the postoperative analgesic and recovery effect of TAPB combined with RSB and ESPB in patients undergoing laparoscopic hepatectomy.

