### **3.2 Random grouping**

Patients were randomly divided into two groups according to computer generate random number table: TAPB combined with RSB group (control group) and ESPB group (experimental group). Group assignment information was stored in a sealed opaque envelope and stored and distributed by a specific person.

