### **5. Sample estimation**

The sample size was calculated based on previous literature, requiring 27 patients per group to achieve a two-sided 0.05 significance level and 90% power of the test. A sample size of 60 was required to set a dropout rate of 10%.

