# **8.Data collection and statistical analysis**

## **8.1 Data collection**

Main observation indicator: consumption of morphine within 24 hours after surgery

Secondary observation indicators

- 1) Morphine consumption at 1h, 2h, 4h and 8h after surgery

- 2) Number of rescue analgesia at 1h, 2h, 4h, 8h and 24 hours after surgery
- 3) VAS scores in resting and coughing at 1h, 2h, 4h, 8h and 24h after surgery
- 4) CVP values at 5, 10, 15 and 30min after nerve block
- 5) QoR-15 patient questionnaire scores before and 24h after surgery
- 6) Postoperative liver function (the percentage increase of AST and ALT compare with preoperative), postoperative complications and discharge time

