## **8.2 Statistical analysis**

The Shapiro Wilk test was used to determine the normality of data distribution for measurement data. Measurement data with normal distribution were expressed as mean  $\pm$  standard deviation, and measurement data with non-normal distribution were expressed as median (interquartile range, IQR). Measurement data were compared between groups by t test or Mann-Whitney U test according to whether the data were normal distribution, and VAS scores were compared by repeated measures analysis of variance. Count data were expressed as frequency (%), and compared between groups by using chi-square test or Fisher exact test. The value of P less than 0.05 was considered statistical significance.

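### Section 8.2 applies unadjusted P<0.05 to one primary and about 20 correlated secondary tests, with no hierarchy or exploratory label, and the recovery half of the purpose rests only on those secondaries

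*Combined protocol and SAP*

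**What the plan says.** The combined protocol and SAP states a purpose with two halves, analgesia and recovery (section 2): "Comparing the postoperative analgesic and recovery effect of TAPB combined with RSB and ESPB in patients undergoing laparoscopic hepatectomy".

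Section 8.1 names one primary: "Main observation indicator: consumption of morphine within 24 hours after surgery". It then lists six groups of secondary indicators. The first is "Morphine consumption at 1h, 2h, 4h and 8h after surgery". The others are rescue analgesia at five times, VAS at rest and on coughing at five times, CVP at four times, QoR-15, and a last group holding AST and ALT change, complications and discharge time.

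Section 8.2 assigns t or Mann-Whitney tests to measurements, repeated measures ANOVA to VAS, and chi-square or Fisher tests to counts. It ends: "The value of P less than 0.05 was considered statistical significance". The documents contain no multiplicity adjustment, no testing order and no statement that secondary results are exploratory.

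Section 5 sizes the trial, "requiring 27 patients per group to achieve a two-sided 0.05 significance level and 90% power of the test", and reaches 60 patients after a 10% dropout allowance. The interim look in section 7.3 concerns deaths and complications; no efficacy look is described.

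**The concern.** Naming one primary settles what the analgesic conclusion rests on. It does not settle the recovery conclusion, because no recovery outcome is primary and none is singled out among QoR-15, AST, ALT, complications and discharge time. Under the rule as written, whichever of these five crosses 0.05 may be called significant and offered as the answer to half of the stated purpose.

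The analgesic half has a milder form of the same problem. Pump dose is read at 1 h (section 6, step 9) and at 2, 4, 8 and 24 h (step 10). If these readings are cumulative, the early totals are parts of the primary total. A null 24 h result could then appear beside a significant 2 h or 4 h result, with nothing in the plan to rank them.

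**Working it through.** **1. The plan's own figures.** 27 × 2 = 54, and 54 / (1 − 0.10) = 60, so the step to 60 reproduces. The 27 itself cannot be reproduced, because section 5 says only "The sample size was calculated based on previous literature" and gives no difference or SD. The plan states no family-wise error rate to compare with.

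**2. Count of secondary tests (sections 8.1 and 8.2).**

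| Outcome | Tests |
|---|---|
| Consumption at 1, 2, 4, 8 h | 4 |
| Rescue analgesia at 1, 2, 4, 8, 24 h | 5 |
| VAS at rest and on coughing, one repeated measures analysis each | 2 |
| CVP at 5, 10, 15, 30 min | 4 |
| QoR-15 at 24 h (the preoperative score is a baseline) | 1 |
| AST, ALT, complications, discharge time | 4 |
| **Total** | **20** |

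CVP is neither an analgesic nor a recovery outcome, so 20 − 4 = 16 tests bear on the stated purpose. Of these, 5 concern recovery: QoR-15, AST, ALT, complications and discharge time.

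**3. Chance of at least one P<0.05 when the blocks are identical.** With k independent tests:
- Either direction: 1 − 0.95^k. This gives 0.64 for k = 20, 0.56 for k = 16 and 0.23 for k = 5.
- In favour of ESPB only: 1 − 0.975^k. This gives 0.33 for k = 16 and 0.12 for k = 5.

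The outcomes are surely correlated, and the documents give no correlations. I therefore simulated equicorrelated normal test statistics at assumed values of the pairwise correlation:

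| Correlation | 20 tests, either direction | 16 tests, either direction | 16 tests, favouring ESPB | 5 recovery tests, either direction |
|---|---|---|---|---|
| 0 | 64% | 56% | 33% | 23% |
| 0.3 | 54% | 47% | 24% | 21% |
| 0.5 | 42% | 37% | 19% | 18% |
| 0.7 | 29% | 26% | 13% | 15% |

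**4. A structured alternative.** Suppose cumulative totals at times s < t correlate as √(s/t), rest with cough VAS at 0.7, CVP times at 0.8, AST with ALT at 0.8, and complications with discharge at 0.4. Let a shared correlation among the analgesic outcomes and QoR-15 run from 0 to 0.8. The chance of any significant result among the 20 secondaries then runs from 0.545 down to 0.383, inside the range above.

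**5. Why not one Bonferroni family.** With 27 per group at 90% power, the implied standardised difference is (1.960 + 1.282) × √(2/27) = 0.88. Putting all 21 tests in one family gives 0.05/21 = 0.00238 each. Power for the primary falls to about 58% (normal approximation; 55% with the t test), and about 48 per group would be needed to restore 90%. Labelling and ordering cost none of this.

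**The case against.** The strongest reply is that the confirmatory inference is already sound. One primary is named, the trial is sized for it at two-sided 0.05, and nothing says a secondary may replace a null primary. Unadjusted supportive secondaries are accepted practice. This stands as far as the primary goes: a reader might infer that its error rate is inflated, and it is not. It does not cover recovery, which has no primary, and the label that would make the secondaries merely supportive is missing.

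A reader might also infer that a chance analgesic or recovery benefit for ESPB is more likely than not. The documents do not support that. The 64% figure needs independence, includes CVP and counts both directions. Without CVP and in one direction the range is 13% to 33%.

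Testing VAS at each time would raise the count to 20 − 2 + 10 = 28 and the independent figure to 1 − 0.95^28 = 76%. Section 8.2 names repeated measures ANOVA instead, so that figure describes an analysis not in the plan.

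Two smaller points stand:
- Section 8.1 lists consumption at given hours and does not say it is cumulative. Nesting in the primary is the natural reading, not a stated fact.
- Fisher's test is conservative. At 30 per group its true two-sided error is about 0.9% at an assumed 10% event rate and 2.2% at 20%, so complications may contribute less than 5%.

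**Conclusion.** The point holds as a gap in control of the secondary claims. It is not a defect in the primary test. Under the written rule, the chance of a spurious significant secondary is several times the nominal 5% at every correlation examined, and the recovery conclusion has no protection against it. The sizes are 29% to 64% for any of 20 secondaries; 26% to 56% for the 16 analgesic or recovery ones in either direction and 13% to 33% in favour of ESPB; and 15% to 23% for the 5 recovery outcomes in either direction. They rest on assumed equal correlations between 0 and 0.7 and on each test having exactly 5% error. The count of 20 and the absence of any order or label come directly from the text. The plan should be changed before unblinding.

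**What to change.** Replace the last sentence of section 8.2 with a rule to this effect: only 24 h consumption is tested confirmatorily, at two-sided 0.05; all secondary outcomes are reported as between-group differences with 95% confidence intervals, labelled exploratory, with no claim of an established effect.

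If the sponsor wants a confirmatory recovery claim, add a sentence naming one recovery outcome before unblinding, to be tested at two-sided 0.05 only if the primary is significant. QoR-15 at 24 h is a natural choice, since section 6, step 10 uses it to evaluate recovery, but another outcome would serve if fixed in advance. It would also help to state in section 8.1 whether consumption and rescue counts are cumulative.

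The cost is one or two sentences on testing; N stays at 60 and the primary alpha at 0.05. An isolated P<0.05 on another secondary could no longer be presented as established. With the ordered option, a null primary would also close off the confirmatory recovery test.

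### Section 8.2 plans no between-group difference with a 95% confidence interval, so a non-significant P value alone would not show which differences between the two blocks are excluded

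*Combined protocol and SAP*

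**What the plan says.** The aim in section 2 is comparative: "Comparing the postoperative analgesic and recovery effect of TAPB combined with RSB and ESPB in patients undergoing laparoscopic hepatectomy". Section 8.1 names the primary outcome: "Main observation indicator: consumption of morphine within 24 hours after surgery".

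Section 8.2 holds the whole analysis plan. For each arm it gives mean and SD, median and IQR, or frequency and percentage. The between-group tests are the t test or Mann-Whitney U (chosen by Shapiro-Wilk), repeated measures ANOVA for VAS, and chi-square or Fisher for counts. It closes with the criterion "The value of P less than 0.05 was considered statistical significance". Neither this section nor any other plans an estimated difference or a confidence interval.

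On size, section 5 says "The sample size was calculated based on previous literature", "requiring 27 patients per group to achieve a two-sided 0.05 significance level and 90% power of the test", and allows 10% dropout to reach 60. It gives no difference, SD or test. No margin or minimal important difference appears anywhere.

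**The concern.** Comparing the effects of two active techniques is a question about how large the difference is and how precisely it is known. A P value answers neither part. If the primary comparison gives P≥0.05, the planned output will not say whether the data rule out a worthwhile difference or are still compatible with one. Because the plan states no target difference or margin, a reader also has nothing to set the result against.

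The gap is widest if the morphine data fail the normality test. The planned output is then two medians, two IQRs and a Mann-Whitney P value. The shift that corresponds to that test is the median of all pairwise between-group differences. Neither it nor its interval can be recovered from medians and IQRs; at best a reader could approximate them.

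**Working it through.** **Inputs.** From section 5: two-sided alpha 0.05, power 90%, 27 per group, dropout 10%, total 60. Not in the documents: target difference, SD, test used for sizing. Assumed for illustration: two-sample t test, common SD, all differences in SD units.

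**1. The plan's own figure.** The dropout step reproduces: 27 / 0.90 = 30 per group, 60 in total. The 27 itself cannot be reproduced, because no difference or SD is given. It can only be solved backwards.

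**2. Implied target at 27 per group.**
- Normal formula: d = (1.960 + 1.282) × √(2/27) = 3.242 × 0.2722 = 0.88.
- Noncentral t, solved for 90% power: d = 0.899.
- Allowing for rounding up to 27, the range is 0.88 to 0.90 (normal) or 0.90 to 0.92 (noncentral t). I use 0.90.

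**3. Precision.** Half-width of the 95% CI = t(0.975, 2n−2) × √(2/n).
- n = 27: 0.546 SD.
- n = 30: 0.517 SD.

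**4. What non-significant results would look like at 27 per group.**

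| Observed difference (SD) | 95% CI (SD) | P | Is 0.90 SD excluded? |
|---|---|---|---|
| 0 | −0.55 to 0.55 | 1.0 | yes |
| 0.20 | −0.35 to 0.75 | 0.47 | yes |
| 0.35 | −0.20 to 0.90 | 0.20 | borderline |
| 0.50 | −0.05 to 1.05 | 0.07 | no |

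The interval contains the implied target when the observed difference is at least 0.899 − 0.546 = 0.353 SD. The result is non-significant up to 0.546 SD. So the ambiguous band is about 0.35 to 0.55 SD at 27 per group. With 30 per group it runs from 0.899 − 0.517 = 0.382 to 0.517, or about 0.38 to 0.52 SD.

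**5. Chance of a non-significant result at 27 per group, by assumed true difference.** 0.5 SD: 56%. 0.65 SD: 35%. 0.8 SD: 18%. 0.9 SD: 10%. These are scenarios; the documents do not say which applies.

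All four rows of the table receive the same label under the P<0.05 criterion. The estimate with its interval separates them.

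**The case against.** The strongest reply is that this is mostly a reporting matter. If the t test is used, mean, SD and group size let any reader compute the difference and its 95% CI; frequencies allow the same for a risk difference. A 95% CI excluding zero is then the same decision as P<0.05, so no verdict of significance would change. This is correct, and it limits the point. It does not cover the Mann-Whitney case, and it leaves the main result of a comparative trial for the reader to derive.

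Some stronger readings are tempting, but the documents do not support them:

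- *A non-significant result could not be told apart from a missed large difference.* The per-arm summaries often allow it, and at 90% power a true difference of about 0.9 SD would be missed only about 10% of the time. The exposure lies more with moderate differences.
- *P≥0.05 is the likely outcome because both arms receive an active block.* That depends on an assumed true difference of about 0.5 SD or less. Section 1 describes three comparisons of ESPB with TAPB, all favouring ESPB, and none against TAPB plus RSB. The effect here is unknown.
- *The investigators would report no difference.* Section 8.2 defines significance and is silent on how a non-significant result will be read. It does not prescribe the error.
- *Any non-significant result would be compatible with the target.* Only the band in step 4 is.
- *P<0.05 is the only decision rule in the plan.* Section 7.3 has a separate interim safety stopping rule. P<0.05 is the only criterion for the efficacy comparisons.

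**Conclusion.** The point holds as a gap in estimation. No between-group difference with a 95% CI is planned for the primary or any other outcome, so a non-significant P value would not by itself show which differences are excluded. With the Mann-Whitney test, the planned summaries cannot make up for this.

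The size is illustrative. It rests on a t test, a common SD and a target of about 0.90 SD that is inferred from 27 per group and 90% power, not stated in the plan. On that basis the interval reaches about 0.55 SD either side of the estimate. A non-significant observed difference of roughly 0.35 to 0.55 SD leaves the inferred target open, and one near zero excludes it. The change is worth making because it determines what a non-significant result can say about the stated aim. It does not affect the validity of the tests or the sample size.

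**What to change.** In section 8.2:

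- Make the primary result the difference in 24-hour morphine consumption, ESPB minus TAPB+RSB, with its 95% CI: the mean difference with the t test, or the Hodges-Lehmann shift with the Mann-Whitney test.
- Report a between-group estimate with 95% CI for the secondary outcomes too, using risk differences for binary ones.
- Add a sentence such as: *P≥0.05 will not be interpreted as equal effect; the conclusion will rest on which differences the 95% CI excludes.*

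In section 5, state the target difference, the SD and the test behind the 27 per group. Without a stated target, the interval has no benchmark.

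The cost is a few lines of text and standard software output. No patients, data or change in sample size are needed.
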